## **4 SELECTION AND ENROLLMENT OF PARTICIPANTS**

### **4.1 Inclusion Criteria**

During the online MBDC registration process, CPs will be asked yes/no questions to determine eligibility based on the inclusion/exclusion criteria. Branching logic within the survey will prompt messaging for those are ineligible and trigger an exit from the registration process. In addition, instructors will confirm eligibility of CPs during the check-in calls.

Participants must meet all the following inclusion criteria to participate in this study

- Age  $\geq 18$  years
- Self-identify as being an informal CP providing caregiving to a PLWD
- Register for an MBDC course through the Presence Care Website

### **4.2 Exclusion Criteria**

All candidates meeting any of the exclusion criteria at baseline will be excluded from study participation.

- Previous participation in an MBDC program.
- Does not speak and understand either English.

### **4.3 Study Enrollment Procedures**

**Recruitment:** Each pilot site has an established Presence Care certified instructor with 3-7 years of experience teaching MBDC to CPs referred by the memory clinic in their health system. In preparation for a future larger study, we will train one new MBDC instructor as part of this pilot. MBDC courses are ongoing, with systems in place at each site for referring CPs, and classes being held virtually due to the COVID-19 pandemic. Participants will be referred from memory care clinics at each of the three aligned healthcare settings using flyers. Flyers are handed out by clinicians (physicians, advance-practice providers, neuropsychologists) during clinic visits to those CPs they feel would benefit from the program. Referrals using flyers at clinics may also occur during conversations with non-clinician staff (social work, Care Ecosystem). Flyers are posted on the clinic website and public spaces in the clinic. Partnerships with community-based programs surrounding the pilot sites are also in place including sharing MBDC flyers with local day programs and the Alzheimer's Association. Interested CPs referred to the MBDC program will visit the Presence Care website to register using the centralized system.

In addition to the current practices above, this pilot will use additional strategies to maximize the participation of diverse CPs in our communities. In addition, at HealthPartners, we will request a waiver of consent to identify PLWD through the electronic health record and healthcare claims data, and mail letters with MBDC flyers to families with over-sampling of non-white and Hispanic patients. The study team programmer will identify patients using ICD-10 diagnostic codes for dementia or mild cognitive impairment (F00-F03, G30-G31.9) documented at least two outpatient or inpatient encounters or if present on to the problem list (a list of diagnoses on a patient's electronic health record dashboard) in the electronic health record. At HealthPartners, patients can opt out of use of their data for research. We will exclude patients from mailings who have declined permission for their medical records to be used in research. CPs interested in participating will be directed to visit the Presence Care website to register using the centralized system.

**Randomization scheme:** As described above in Section 3, at the time of enrollment (registration on the Presence Care site), a CP will be presented with several currently enrolling class options (multiple days/times of week) and asked to select two that work with their schedule. They will then be randomly enrolled in one of the two selected courses, allowing for randomization on the class level while still accommodating the participant's schedule.

**Consenting:** Participation in the MBDC program will be completely voluntary. We plan to seek a waiver of informed consent for all aspects of the study. Please see section 11.2 for details.

## **5 STUDY INTERVENTIONS**

### **5.1 Interventions, Administration, and Duration**

MBDC group sessions will be held virtually via web-based video calls with a phone option available. Presence Care certified instructors will facilitate the sessions and use the MBDC participant Workbook (Appendix 1). Nine sessions including 8 weekly classes (2 hours each) and a half-day retreat (4 hours) will cover several topics (Table 1).

The core course content for each session will be recorded for individuals who are unable to attend. As taught in the Presence Care certification, instructors will reach out to CPs that miss class sessions with an informal email including a link to the recording. CPs will be asked to watch the session and send the instructor a brief summary about the content in order to make up the session. CPs will be emailed one chapter of the MBDC workbook for each class (Appendix 1). The CP workbook is currently available in English for in-person and virtual classes. Presence Care is currently in the process of updating the in-person Spanish MBDC workbook for the virtual class mode. Upon completion of the course, participants will be offered the opportunity to participate in a variety of mindfulness maintenance activities, such as weekly, guided virtual group meetings of MBDC graduates.

### **5.2 Handling of Study Interventions**

Instructors are already trained and certified by Presence Care Project. All instructors will

use the MBDC participant workbook (Appendix 1). Class attendance will be recorded by instructors in the REDCap database.

### **5.3 Concomitant Interventions**

#### 5.3.1 Allowed Interventions

*Not Applicable*

#### 5.3.2 Required Interventions

*Not Applicable*

#### 5.3.3 Prohibited Interventions

Previous participation in an MBDC program.

### **5.4 Adherence Assessment**

Adherence to the intervention is defined as attendance of >75% of classes (or watching video makeup) for at least 6 of 9 sessions.

## 6 STUDY PROCEDURES

### 6.1 Schedule of Study Activities

Assessment	Registration (Q1)	Randomization	Instructor Check-In	Pre-Course Survey (Q2)	MBDC Course	Post-Course Survey (Q3)	Follow-Up Survey (Q4)
Timing		4 wk before course	2-3 wk before course	Sent 10 days before course		Sent 3 days after course	Sent 3 mo after course
Inclusion/Exclusion Criteria Participation Questions on Website	X		X				
Course Registration (CP, contact info, referral source, demographics, caregiving info, PLWD info, preferred course times/dates)	X						
Clinical Outcome Scales	X			X		X	X
CP Behavior Change Measures	X			X		X	X
Assignment to Course (course information)		X					X
Check-in with Instructor			X				
Course Attendance					X		
Course Satisfaction						X	
Assessment of Willingness to Share Healthcare Claims Access						X	
REDCap Automated Data Collection (dates of registration, randomization, questionnaire completion, etc.)	X	X	X	X	X	X	X
Adverse Events	X	X	X	X	X	X	X

## 6.2 Description of Evaluations

There are no research visits in this pragmatic trial. Below we describe the administrative data collection occurring as part of course registration and follow-up.

### 6.2.1 Screening Evaluation

#### Registration

Care partners referred using flyers that are interested in the MBDC program will be directed to register on the Presence Care website. The website will contain information about the MBDC course and what is expected for participation. It will also include screening questions regarding the inclusion/exclusion criteria. When CPs confirm their interest, they will be directed to answer questions regarding their demographics, contact information, referral source, caregiving information, PLWD information, and preferred course times/dates. Next, there will be questionnaires that include the clinical outcome scales and behavior change measures.

In this pragmatic clinical trial, enrollment is considered the act of completing registration for MBDC on the Presence Care Website.

There is a variable time period between CP registration and randomization. In this pilot, we also include a phone option for registration with a staff member. For this pilot, we will use a HealthPartners research staff member to speak with CPS and enter the information given to them verbally into the Presence Care website registration link. We will assess the use of these phone services to determine if this is mode is needed for the full scale ePCT.

### 6.2.2 Enrollment, Baseline, and/or Randomization

#### Randomization

Four weeks before a course is scheduled to start, CPs will be randomized to attend one of the two indicated as preferred days/times. They will be contacted by email of their assignment or by phone if that was the mode of registration. If a CP declines the assigned MBDC course, they will be given the option to choose their preferred day and time. We are assessing the feasibility of randomization and do not want to withhold the MBDC program from those for whom this is not feasible.

#### Instructor Check-In

About two or three weeks prior to the course initiation, instructors will contact participants for a brief phone call (approximately 15 min) to discuss the MBDC program. They will review the inclusion/exclusion criteria, ensure the program is a good fit, and confirm that the CP understands the time commitment involved. These check-ins are a normal part of teaching MBDC.

#### Pre-Course Survey

Ten days prior to course initiation, CPs will receive an email with a link to a questionnaire. There will be 3 automated reminders (every 3 days) if the survey is not

completed. HealthPartners research staff will similarly call CPs who registered via phone to obtain that data.

#### MBDC Course Participation

CPs will participate virtually in the live MBDC courses. Each course consists of nine sessions including 8 weekly classes and a 4-hour retreat. An extended session, like a retreat, is a protocolized part of any Mindfulness-Based curriculum. In our experience, attendance for this session is strong, and participant feedback is quite positive. Based upon stakeholder feedback, we have reduced the regular 8-hour retreat to a 4-hour session. During the pandemic, we found that the online version of this retreat is powerful in a different way than the in-person version. MBDC offers a bridge between mindfulness practice and the dementia care exchange. Participants find that they can practice in their own home, with their loved one present, and often intermittently interrupting. During the sessions, care partners are encouraged to include any disruptions and challenges in everyday life and caregiving, and to practice right where they are, as they are with no special conditions needed. In this pilot, we will evaluate the retreat, reasons why not attended, and add a question about the retreat length to the course satisfaction survey. We will be able to adapt through the phased implementation of the courses, to find the best length to meet the needs of care partners in preparation for the implementation of a full scale ePCT.

#### 6.2.3 Follow-up Visits

##### Post-Course Survey (Q3)

Three days after course completion, CPs will receive an email with a link to a questionnaire. This survey will include clinical outcome scales and behavior change measures in addition to course satisfaction questions and healthcare claims access questions. There will be 3 automated reminders (every 5 days) if the survey is not completed. Research assistants will call CPs who registered via phone to obtain the data.

After the conclusion of all MBDC courses, the study team will conduct a one-hour interview with the director of the specialty clinic at each Memory Clinic Directors. Topics of conversation will include their perspectives on recruitment for MBDC in the clinic and opportunities for improving processes.

#### 6.2.4 Completion/Final Evaluation

##### Follow-Up Survey (Q4)

Three months after course completion, CPs will receive an email with a link to a questionnaire. In the survey, there will be a statement of implied consent prior to the clinical outcome scales and behavior change measures. There will be 3 automated reminders (every 5 days) if the survey is not completed. Staff will call CPs who registered via phone to obtain the data.

## **7 SAFETY ASSESSMENTS**

### **7.1 Specification of Safety Parameters**

This pragmatic study has limited data available for safety parameters. We will monitor depressive symptoms and caregiver burden measured as part of the administrative data. If significant increases are observed between registration and the pre-course questionnaire, we will discuss whether the delay period is detrimental to CPs. If significant increases are observed between the pre and post course surveys (the opposite results than we expect), we will discuss whether MBDC implemented in this manner is either not effective or doing harm and make changes.

### **7.2 Methods and Timing for Assessing, Recording, and Analyzing Safety Parameters**

There is a small potential for increased stress as a part of participation in the MBDC program. There is a rare chance that instructors may encounter CPs with exhibiting concerning levels of stress or anxiety. Instructors will reach out to these individuals and document this as an AE in the REDCap database. As part of their teaching responsibility, instructors obtain emergency contact information and the address of CPs in the rare case it is needed during MBDC sessions.

### **7.3 Adverse Events and Serious Adverse Events**

**AE Definition:** AE is any untoward or unfavorable medical occurrence in a human study participant, including any abnormal sign (e.g. abnormal physical exam or laboratory finding), symptom, or disease, temporally associated with the participants' involvement in the research, whether or not considered related to participation in the research.

**SAE Definition:** SAEs consist of any adverse event that results in death; is life threatening or places the participant at immediate risk of death from the event as it occurred; requires or prolongs hospitalization; causes persistent or significant disability or incapacity; results in congenital anomalies or birth defects; is another condition which investigators judge to represent significant hazards.

**Unanticipated Problem (UP) Definition:** any incident, experience, or outcome that meets all the following criteria:

- unexpected, in terms of nature, severity, or frequency, given (a) the research procedures that are described in the protocol-related documents, such as the IRB-approved research protocol and informed consent document; and (b) the characteristics of the study population;
- related or possibly related to participation in the research;
- suggests that the research places participants or others at a greater risk of harm (including physical, psychological, economic, or social harm) than was previously known or recognized.

**AEs for this study include:** No AEs are expected. More than 150 CPs have completed the MBDC program with no reports of adverse events. There is a small potential for increased stress as a part of participation in the MBDC program.

**SAEs for this study include:** No SAE are expected. More than 150 CPs have completed the MBDC program with no reports of adverse events.

**Process for identifying AEs, SAEs, and UPs:** AEs, SAEs and UPs related to participation in the MBDC program will be collected by the instructors and entered into the Presence Care website database (REDCap system) where CP participation, such as attendance is collected. Entry of AEs, SAEs, and UPs will trigger an alert to the PI who will evaluate (and investigate if necessary), then categorize its severity, expectedness, and potential relatedness.

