### **Reporting schedule:**

- All adverse events that are serious (SAE) and unexpected (i.e., have not been previously reported for the study's intervention) will be reported to the IMPACT Collaboratory Regulatory and Data Team Leader ([name]), NIA IMPACT Collaboratory PO ([name]), and the IMPACT Collaboratory Safety Officer within 48 hours of the study's knowledge of SAE.
- Only those adverse events that are serious (SAE), unexpected, and related to the intervention must also be reported to Advarra IRB. Unexpected and unrelated SAEs will be reported to Advarra IRB on a case-by-case basis if requested by the IMPACT Collaboratory Safety Officer or NIA IMPACT Collaboratory PO.
- All deaths will be reported to IMPACT Collaboratory Regulatory and Data Team Leader ([name]), NIA IMPACT Collaboratory PO ([name]), and the IMPACT Collaboratory Safety Officer within 24 hours of study's knowledge of death.
- Advarra IRB does not require the specific reporting of death outside of the SAE reporting requirement above, but they will be notified on a case-by-case basis if requested by the IMPACT Collaboratory Safety Officer or NIA IMPACT Collaboratory PO.
- All unanticipated problems (UPs) will be reported to the IMPACT Collaboratory Regulatory and Data Team Leader ([name]), Advarra IRB, NIA IMPACT Collaboratory PO ([name]), and the IMPACT Collaboratory Safety Officer within 48 hours of the study's knowledge of the event.
- The summaries of all previously reported unexpected and related SAEs, deaths, and UPs, as well as all other SAEs and AEs will be reported to IMPACT Collaboratory Regulatory and Data Team Lead ([name]), Advarra IRB, NIA IMPACT Collaboratory PO ([name]), and the IMPACT Collaboratory Safety Officer at a minimum every 6 months, or at a frequency requested by the IMPACT Collaboratory Safety Officer or NIA IMPACT Collaboratory PO.

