### Relatedness

- **Definitely Related:** The adverse event is clearly related to the investigational agent/procedure – i.e. an event that follows a reasonable temporal sequence from administration of the study intervention, follows a known or expected response pattern to the suspected intervention, that is confirmed by improvement on stopping and reappearance of the event on repeated exposure and that could not be reasonably explained by the known characteristics of the subject's clinical state.
- **Possibly Related:** An adverse event that follows a reasonable temporal sequence from administration of the study intervention follows a known or expected response pattern to the suspected intervention, but that could readily have been produced by a number of other factors.
- **Not Related:** The adverse event is clearly not related to the investigational agent/procedure - i.e. another cause of the event is most plausible; and/or a clinically plausible temporal sequence is inconsistent with the onset of the event and the study intervention and/or a causal relationship is considered biologically implausible.

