#### 7.3.2 Follow-up for Adverse Events

The occurrence of an adverse event (AE) or serious adverse event (SAE) may come to the attention of the instructor during MBDC program classes. Instructors will capture these events in the REDCap database and follow-up as needed with CP participants.

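### Section 7.3 limits instructor collection to events related to MBDC, although the plan defines, grades and reports events regardless of relatedness, and no one is assigned to capture AEs for most of the wait or the follow-up

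*Combined protocol and SAP*

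**What the plan says.** All references are to the combined protocol and SAP.

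- **Definition (7.3).** An event counts as an AE "whether or not considered related to participation in the research".
- **Collection (7.3, process paragraph).** "AEs, SAEs and UPs related to participation in the MBDC program will be collected by the instructors"; the record is made in REDCap. Entry alerts the PI, who evaluates the event, "then categorize its severity, expectedness, and potential relatedness".
- **Grading (7.3.1, Relatedness).** The lowest of the three categories reads "The adverse event is clearly not related to the investigational agent/procedure".
- **Capture in class (7.2 and 7.3.2).** Under 7.3.2, an AE or SAE "may come to the attention of the instructor during MBDC program classes", and instructors record it in REDCap. Section 7.2 has them document concerning stress or anxiety as an AE. Neither section sets a relatedness condition.
- **Reporting (7.3, Reporting schedule).** On expedited SAEs: "All adverse events that are serious (SAE) and unexpected (i.e., have not been previously reported for the study's intervention) will be reported". Recipients are named at the IMPACT Collaboratory and NIA, and the limit is 48 hours. On deaths: "All deaths will be reported to IMPACT Collaboratory Regulatory and Data Team Leader". Other recipients are named there too, and the limit is 24 hours. Both clocks start when the study learns of the event. Summaries covering all other SAEs and AEs follow at least every 6 months. Expedited SAE reporting to the IRB is confined to serious, unexpected and related events; unrelated ones go there only on request.
- **Schedule (6.1).** The row "Adverse Events" is marked in all seven columns: registration (Q1), randomization, instructor check-in, Q2, the course, Q3 and Q4.

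**The concern.** The collection sentence places a causality judgment with the instructor, ahead of the step at which the plan gives that judgment to the PI. Section 10.3.1 describes instructor training in REDCap data entry and does not mention causality assessment. An instructor who follows 7.3 literally would leave out an event thought to be unrelated. An instructor who follows 7.3.2 would enter it. Both could cite the protocol.

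The schedule adds a second problem. It promises AE collection from registration to the last survey, but the procedures describe only what instructors notice.

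At stake is how a low or zero AE count can be read. Sections 7.3 and 11.2 both cite the absence of reported adverse events so far, and 11.2 uses it to support the minimal-risk argument for the consent waiver. The pilot is meant to guide a full-scale trial (Section 3). Under 9.3, the Safety Officer and NIA may stop the study after reviewing data supplied by the statistician, and those data can hold only what was entered.

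**Working it through.** **Step 1. What each part of the plan needs from collection.**

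| Place | What it needs | Fits a related-only entry rule? |
|---|---|---|
| 7.3, AE definition | events whatever their cause | no |
| 7.3, PI review after entry | ungraded events | no, since grading would come after filtering |
| 7.3.1, Not Related category | unrelated events on file | no, the category would be largely empty |
| 7.2 and 7.3.2, instructor capture | events noticed, no condition | no |
| Reporting schedule, 48 hours | all serious unexpected events | no |
| Reporting schedule, 24 hours | all deaths | no |
| Reporting schedule, 6-monthly | all other SAEs and AEs | no |
| Reporting schedule, expedited SAEs to the IRB | serious, unexpected, related events | yes |

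Seven of the eight rows need events without a relatedness filter.

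**Step 2. Can the qualifier be read as applying to UPs alone?** Grammatically, yes. But the UP definition in 7.3 already requires that the event be related or possibly related, so on that reading the qualifier would add nothing. The natural reading covers AEs, SAEs and UPs.

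**Step 3. Schedule against procedures.** Instructors are the only collectors named (7.2, 7.3, 7.3.2). They have contact in two of the seven marked columns, the check-in call and the course. If everything from check-in to course end is counted, Q2 also falls inside, because it is sent 10 days before the course. Registration, randomization (4 weeks before), Q3 (3 days after) and Q4 (3 months after) stay outside. The contents of Q1 to Q4 in the data elements table of Section 3, and the survey descriptions in 6.2, list no AE item.

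**Step 4. Calendar share of instructor contact.** The plan states no coverage figure, so there is none to reproduce. Inputs:

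- Total participation: about 7 months (Précis, Section 3).
- Course: 8 weeks (Précis, Section 3), or nine weeks (2.2).
- Check-in call: 2 to 3 weeks before the course (6.1, 6.2.2).
- Follow-up: 3 months.

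One month = 365.25 / 12 / 7 = 4.348 weeks, so 7 months = 30.4 weeks. Share = weeks of contact / 30.4.

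- 8-week course alone: 8 / 30.4 = 26%.
- 9-week course alone: 9 / 30.4 = 30%.
- 8-week course, counted from check-in: 10 / 30.4 = 33% to 11 / 30.4 = 36%.
- 9-week course, counted from check-in (most generous): 11 / 30.4 = 36% to 12 / 30.4 = 39%.

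The total is approximate because the wait varies. Assuming 6 to 8 months in all, the 8-week course alone covers 31% to 23%.

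**Step 5. Where the uncovered time lies.** Follow-up = 3 x 4.348 = 13.0 weeks. Implied wait = 30.4 - 8 - 13.0 = 9.4 weeks, of which the check-in window takes 2 to 3. That leaves 6.4 to 7.4 weeks of the wait and all 13.0 weeks of follow-up, or 19.4 to 20.4 of 30.4 weeks (64% to 67%), without a named collector.

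**The case against.** The best defence is that this is a minimal-risk pragmatic study with no research visits (6.2), that 7.1 openly says safety data are limited, and that passive capture is a deliberate choice. Safety is neither a primary nor a secondary outcome (9.4), and 9.5 contains no AE analysis. All of that stands, and it keeps the point to one of wording and ascertainment. It does not reconcile the sections with each other.

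Four stronger readings are tempting, and the documents do not support them.

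- *Instructors collect related events and nothing else.* Sections 7.2 and 7.3.2 have them record events with no relatedness condition. The plan is inconsistent on this point; it is not uniformly restrictive.
- *The 24- and 48-hour duties will be breached.* The clocks run from the study's knowledge. An event that no one reports to the study starts no clock.
- *Unrelated SAEs must go to the IRB on an expedited basis.* They go there only on request. The unconditional expedited duties run to the IMPACT Collaboratory and NIA recipients.
- *About three quarters of events will be missed.* The 74% outside an 8-week course (1 - 8 / 30.4) is calendar time, not a share of events. The documents give no event rates, and the figure leaves out the check-in call.

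Other contacts do exist: update emails during the wait (9.2.1), staff calls to phone registrants at Q2, Q3 and Q4 (6.2), and optional graduate meetings (Section 3, 5.1). Events could become known through them, but none is given an AE task. The CES-D-10 and burden monitoring in 7.1 does give some oversight of the wait. It compares scores from registration to pre-course and from pre- to post-course, names no Q4 comparison, and would not reveal a hospitalization or a death.

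**Conclusion.** The concern holds as an internal inconsistency with a practical consequence. The collection sentence in 7.3, followed as written, would filter out events that the same section says will be graded and reported. The schedule in 6.1 promises AE collection for which the plan names no collector or method over most of the pre-course wait and the three-month follow-up. Instructor contact covers about 26% to 36% of the roughly seven months, and 39% at most if the nine-week course and the earliest check-in are both assumed.

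This rests on two assumptions: that the relatedness qualifier covers all three event types (Step 2), and that seven months is a fair typical duration. The contradiction in Step 1 does not depend on the second.

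The effect is incomplete ascertainment of AEs, SAEs and deaths. How many events would be lost cannot be estimated from the documents. No efficacy estimate, sample size, error rate or progression criterion is affected. It should be corrected, because the change costs almost nothing.

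**What to change.** 1. In the 7.3 collection sentence, strike the relatedness qualifier that stands between UPs and the verb. Instructors then enter every event they learn of, and the PI alone assigns relatedness. Cost: one edit, and a few more unrelated events for the PI to classify.
2. Reconcile 6.1, 7.3, the reporting schedule and 7.3.2. The simplest way is to limit the AE row in 6.1, and any safety statement drawn from the study, to the period of instructor contact from check-in through course end. Cost: protocol wording only.
3. As an optional alternative to item 2, keep the wider window and add one AE item to Q2, Q3 and Q4, which are already sent. Cost: a small added survey burden. That has to be weighed against the plan's aim of keeping questionnaires short (9.1) and its argument in 11.2 that extra paperwork could bias the feasibility measures.
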